5.4.2.4 Death, SAE and other significant AE

5.4.2.4.1 Death

The number and percentage of patients who died during different time periods were summarized, and the causes of deaths during treatment were summarized:

- All deaths
- Treatment-emergent deaths, defined as deaths that occurred between the start of study treatment and within 30 days after the end of treatment
- Deaths during the follow-up period, defined as those that occurred at or after 30 + 1 days after the end of study treatment.

In addition, deaths due to AE were summarized by MedDRA SOC (in alphabetical order) and PT (in descending order of incidence).

For confirmed deaths only, the date of death is imputed with the following rules:

- If the year is missing (or all missing), it is imputed with the last known survival date + 1;
- If the month and day are missing, they are imputed with January 1st of the current year;
- If only the day is missing, it is imputed with the 1st of the current month.

The last known survival date is defined as the latest of the following dates:

- All test/examination dates including all laboratory tests, vital sign tests, imaging examinations
- Treatment dates including the date of treatment with the investigational drug, concomitant drugs, concomitant non-drugs
- Onset date of adverse event and end date of adverse event with an outcome other than death
- Date of last survival in which the subject's status is not "dead" on the Survival Follow-up page
- The study completion date on the end of study page or the withdrawal date for which the reason for the withdrawal is not "lost to follow-up" and "death"

If the imputed date of death is before the last known survival date, the imputed date is modified to the last known survival date + 1. If the imputed date of death is after the referencable date of death (date of follow-up visit in which the survival follow-up status is "dead"), the imputed date is modified to the referencable date of death - 1.

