14.1.28 Data handling and programming rules

The following section should be used as guidance for development of the protocol, data handling procedures or programming requirements (e.g. on incomplete dates).

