14.1.29 Study/project specific decisions

For each study (or project) various issues need to be addressed and specified in the protocol or RAP documentation. Any deviations from protocol must be discussed and defined at the latest in the RAP documentation.

The proposed primary analysis and potential sensitivity analyses should be discussed and agreed with the health authorities and documented in the protocol (or at the latest in the RAP documentation before database lock).

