14.1.33 Programming rules

The following should be used for programming of efficacy results:

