14.1.36 Incomplete dates for last known date patient alive or death

All dates must be completed with day, month and year. If the day is missing, the 15th of the month will be used for incomplete death dates or dates of last contact.

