5.3.3 Demographic and Baseline Characteristics

Demographic characteristics and baseline characteristics will be summarized and tabulated based on the FAS.

The following demographic characteristics and baseline characteristics will be summarized and tabulated separately:

Demographic characteristics

- Age and age group (18 to < 65 years, \geq 65 years)
- Gender
- Height
- Weight
- Body mass index (weight (kg) / (height (cm) / 100)²)

Baseline disease characteristics

- Type according to histological diagnosis
- Tumor staging
- Duration of illness (years, time from initial diagnosis to start of study treatment): if the day is missing in the patient's initial diagnosis date (year and month known), it will be imputed using the median value of the dates in that month, i.e., it will be imputed as 15th if that month consists of 30 days, or as 16th if that month consists of 31 days; if the month and day are missing in the patient's initial diagnosis date (year known), it will be imputed with June 30 of that year.

In addition, the following baseline tumor lesion examinations will be summarized by means of contingency tables or descriptive statistics (number of cases, mean, median, standard deviation, minimum, and maximum) according to the distribution of data types:

- Total number of lesions, number of target lesions, and number of non-target lesions (1, 2, 3, 4, 5 and > 5)
- Number of organs affected (1, 2 and ≥ 3)
- Distribution of organs affected
- Type of lesion (only target lesion, both target lesions and non-target lesions)
- Diameter of target lesion (short diameter of the nodular lesion or the longest diameter of other target lesions)

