5.5.5 Additional analysis for assessment the impact of COVID-19

Considering that the outbreak of COVID-19 in 2020 has affected the work of each study site to varying degrees, protocol deviations due to COVID-19 were collected for this study, including visit assessments completed at other hospitals, visit assessments and tests not completed or out-of-window due to COVID-19, changes in drug supply methods, interruption or discontinuation of study drug treatment, etc. Patients seriously affected by COVID-19 were identified at the data review meeting, and patients whose response was seriously affected by COVID-19 were excluded from the sensitivity analysis of efficacy, with the purpose of exploring the potential impact of COVID-19 on the efficacy assessment results of this study.

6 Interim analysis

Interim analysis was conducted during the study as needed. In order to obtain an outline of the data submitted to the China Food and Drug Administration when the drug license was renewed in February 2018, the project team planned to conduct the first interim analysis around July 2017. Moreover, during the study, based on the requirements of the Center for Drug Evaluation, clinical data was submitted every 5 years for license renewal, so the project team planned to conduct the second interim analysis in February 2021.

The contents of the interim analysis included all primary and secondary endpoints covered by the statistical analysis plan. The analytical methods of this study are predominantly descriptive, so alpha spending function is not applicable. For interim analysis, data will be analyzed according to the content and methods of analysis described in this SAP, and there is no plan to formulate a separate SAP of interim analysis.

7 Modification of the Analytical Method for the Protocol Plan

None.

8 Statistical Analysis Form Template Statistics

The analysis form template will be provided in a separate document.

9 Reference

1. Collett, D. (2003), Modeling Survival Data in Medical Research, Second Edition, London: Chapman & Hall.

10 Appendix

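### For a death date with only the day missing, the SAP uses the 1st of the month where the protocol uses the 15th, without declaring the change; OS and PFS death dates then err early only

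*SAP*

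**What the plan says.** Protocol 14.1.36 (Appendix 1): "If the day is missing, the 15th of the month will be used for incomplete death dates or dates of last contact". It gives no rule for a death date that also lacks the month. The programming rules that contain it are introduced in 14.1.33 with "The following should be used for programming of efficacy results".

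SAP 5.4.2.4.1, for confirmed deaths: "If only the day is missing, it is imputed with the 1st of the current month", and "If the month and day are missing, they are imputed with January 1st of the current year". If the year is missing, the date becomes the day after the last known survival date. Two bounds follow. An imputed date earlier than the last known survival date is raised to the day after it (the floor). One later than the follow-up visit that records the death is set to the day before that visit (the cap).

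The same subsection counts a death as treatment-emergent if it falls between the start of treatment and 30 days after its end. SAP 5.5.1 refers to 5.4.2.4.1 only for the last known survival date, but no other death-date rule exists in the SAP.

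SAP Section 7, headed "Modification of the Analytical Method for the Protocol Plan", contains only the word None. The SAP version table shows that death-date imputation was added in Version 3.0 (May 2021).

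**The concern.** The two documents give different answers for the same incomplete date, and the section meant to disclose such changes says there are none. A programmer holding both cannot tell which rule governs OS.

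The SAP rules also err in one direction only. The 1st, January 1 and last-known-alive plus one day are each the earliest date compatible with what is known. The SAP was willing to use central values elsewhere: for a diagnosis date without month and day, "it will be imputed with June 30 of that year".

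At stake are the event time for OS, the event time for PFS when death comes first, and the split between treatment-emergent and follow-up deaths, which belongs to the safety analysis and so to the primary objective.

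**Working it through.** The plan states no figure to reproduce: the sample size rests on feasibility and no rate of incomplete dates is given.

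**Inputs.** The rules and bounds above. Survival contact every 6 months (protocol 4.1), taken as 182 days. Visits every 12 weeks (protocol Table 7-1), 84 days. About 60 patients. Median OS 27 months (protocol 1.1, metastatic pNET), for scale only; 44 months is an added assumption. Error = imputed date minus true date; deaths are uniform over the calendar.

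**1. Without the floor.** Over the 365 days of a non-leap year the mean day of the month is (7×496 + 4×465 + 406)/365 = 5738/365 = 15.72.
- 1st: 1 - 15.72 = -14.7 days (range -30 to 0).
- 15th: 15 - 15.72 = -0.7 days (range -16 to +14).
- January 1: minus the mean of 0 to 364 = -182 days.

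**2. With the floor.** Imputed date = the later of the rule date and last known alive + 1. Last known alive is simulated as uniform over 1 to 84, or 1 to 182, days before death.

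| Rule | No floor | Contact up to 84 days before | Contact up to 182 days before |
|---|---|---|---|
| 1st (day missing) | -14.7 | -12.9 | -13.9 |
| 15th (day missing) | -0.7 | -0.4 | -0.6 |
| January 1 (month and day missing) | -182 | -38.3 | -75.5 |

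Under the 1st and January 1 no simulated date was later than the truth.

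**3. Effect on median OS.** Kaplan-Meier, n = 60, exponential survival, floor applied with contact up to 182 days before death. Mean shift in days, 27-month / 44-month median:

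| Share of deaths incomplete | 1st | January 1 |
|---|---|---|
| 5% | -0.6 / -0.8 | -3.8 / -3.4 |
| 10% | -1.4 / -1.4 | -6.7 / -7.3 |
| 20% | -2.7 / -2.8 | -14.1 / -14.3 |
| 50% | -6.8 / -6.4 | -36.0 / -36.0 |
| 100% | -13.8 / -13.7 | -73.5 / -74.8 |

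Using the 15th moved the median by 0.7 days or less throughout.

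**4. PFS.** The death date matters only when death is the first event (SAP Table 2, row 6). It also enters the 24 + 2 week limits in the notes to Table 2, so an early date can turn a death that would be censored under row 7 into an event.

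**5. Treatment-emergent label.** Let W = last dose + 30 days. Take a death with the day missing, in the calendar month containing W, with last known alive before W. The 1st of that month is on or before W, and last known alive + 1 is on or before W. The later of the two is therefore on or before W, and the label is treatment-emergent in 100% of such cases. With death uniform in that month, the share truly within the window is 50% if last known alive is the day of last dose, and 57% if it is spread between last dose and death. So 43% to 50% truly fall after the window.

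In the first setting the 15th labels 52% treatment-emergent, but individual labels still err: 26.0% are wrong, with a net excess of 2.5 points. Wrongly excluded: (26.0 - 2.5)/2 = 11.75 points, and 11.75/49.9 is about 24% of the truly treatment-emergent deaths. It is about 22% if months in which the window closes on the last day are also counted.

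**The case against.** The strongest reply is that the protocol rule is not binding. It sits in a generic oncology guideline, where 14.1.28 says "The following section should be used as guidance for development of the protocol, data handling procedures or programming requirements" and 14.1.29 says "Any deviations from protocol must be discussed and defined at the latest in the RAP documentation". The SAP does define its rule. This stands in part: the change is permitted. But it is neither identified as a change nor explained, and Section 7 denies that there is one.

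Second, early dating is conservative. It shortens OS and PFS, adds treatment-emergent deaths, and matches other SAP 5.4.2 conventions, such as treating missing causality as related. For the safety label this is a fair defence, since the 15th would move about 22% to 24% of truly treatment-emergent ambiguous deaths out of the window. For OS and PFS, which are descriptive estimates, it is still a bias, and the SAP states no such rationale.

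Third, the practical effect may be small. Missing values are queried with sites (protocol 9.4), the last known survival date draws on many kinds of record, and patients are contacted during the 30 days after last dose. All of this stands.

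A reader might infer three stronger points that the documents do not support:
- That January 1 contradicts the protocol. The protocol has no rule for a missing month, so January 1 fills a gap.
- That the error averages half a year. The -182 days ignores the floor in the same SAP subsection.
- That every death with an incomplete date is labelled treatment-emergent. That holds only under the conditions in step 5; if the patient is known alive on or after the window's last day, the floor moves the death out.

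**Conclusion.** For a missing day there is a real, undeclared conflict between protocol 14.1.36 and SAP 5.4.2.4.1, and the SAP's choice biases the death date early by about 13 to 14 days on average, against less than one day under the protocol's own rule. For a missing month and day there is no conflict, but the SAP rule is early by about 38 to 75 days. These figures assume uniform death dates and last contact up to 84 or 182 days before death.

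The effect on median OS is likely only days: about 1 to 7 if 10% of death dates are incomplete, and more only if many are. The documents do not give that share. The direction makes the drug look worse, so nothing here suggests a favourable tilt. With about 60 patients, one relabelled death changes the treatment-emergent death rate by 1/60 = 1.7 percentage points; the number of deaths in that position is unknown and may be zero.

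**What to change.** In the SAP:

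- State which death-date rule applies to OS and PFS. For those endpoints, use the protocol's 15th when only the day is missing, keeping the existing floor and cap.
- When month and day are missing, use a mid-value within the same bounds. June 30 matches the SAP's diagnosis-date convention. The midpoint between last known alive and the visit recording death, kept within the recorded year, is better: with 6-monthly contact the mean absolute error is about 38 days, against about 60 for June 30 and 75 for January 1.
- If the early date is kept as a conservative rule for classifying treatment-emergent deaths, say so and list it in Section 7.
- Report the number of imputed death dates by type of missing information, and the treatment-emergent death count under both rules.

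The cost is a few lines of SAP text and derivation code. The downside is that individual dates can then be late as well as early: up to 14 days late with the 15th, and up to about 180 days either way with June 30.

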5.4.2.4.2 SAE

The number and percentage of patients with following SAE were tabulated and summarized separately by SOC (in alphabetical order) and PT (in descending order of incidence):

- Treatment-emergent SAE regardless of whether related to the study drug or not
- Treatment-emergent SAE suspected to be related to the study drug
- SAE leading to withdrawal, regardless of whether related to the study drug or not.

The number and percentage of patients with following SAE were tabulated and summarized separately by PT (in descending order of incidence) and CTCAE grade (Grade 3/4):

- Treatment-emergent SAE regardless of whether related to the study drug or not
- Treatment-emergent SAE suspected to be related to the study drug
- SAE leading to withdrawal, regardless of whether related to the study drug or not.

A patient would be categorized and analyzed based on the most severe one if he/she experiences an AE of different severities for many times.

The number and percentage of patients with following SAE were tabulated and summarized separately by SOC (in alphabetical order), PT (in descending order of incidence), and CTCAE grade (all grades):

- Treatment-emergent SAE regardless of whether related to the study drug or not
- Treatment-emergent SAE suspected to be related to the study drug
- SAE leading to withdrawal, regardless of whether related to the study drug or not.

A patient would be categorized and analyzed based on the most severe one if he/she experiences an AE of different severities for many times.

5.4.2.4.3 Other significant AE

Other significant AE included: AE leading to discontinuation of medication, AE leading to withdrawal from the trial, and AE leading to interruption or changes in dose or frequency of Afinitor.

The number and percentage of patients with following significant AE were tabulated and summarized separately by SOC (in alphabetical order) and PT (in descending order of incidence):

- AE leading to discontinuation of medication, regardless of whether related to the study drug or not
- AE leading to withdrawal, regardless of whether related to the study drug or not
- AE leading to interruption or changes in dose or frequency of Afinitor, regardless of whether related to the study drug or not

The number and percentage of patients with following significant AE were tabulated and summarized separately by PT (in descending order of incidence) and CTCAE grade (Grade 3/4):

- AE leading to discontinuation of medication, regardless of whether related to the study drug or not
- AE leading to withdrawal, regardless of whether related to the study drug or not
- AE leading to interruption or changes in dose or frequency of Afinitor, regardless of whether related to the study drug or not

A patient would be categorized and analyzed based on the most severe one if he/she experiences an AE of different severities for many times.

The number and percentage of patients with following significant AE were tabulated and summarized separately by SOC (in alphabetical order), PT (in descending order of incidence), and CTCAE grade (all grades):

- AE leading to discontinuation of medication, regardless of whether related to the study drug or not
- AE leading to withdrawal, regardless of whether related to the study drug or not
- AE leading to interruption or changes in dose or frequency of Afinitor, regardless of whether related to the study drug or not

A patient would be categorized and analyzed based on the most severe one if he/she experiences an AE of different severities for many times.

5.4.3 Laboratory tests

Baseline is defined as the last valid assessment value prior to dosing.

Laboratory test results were converted to International Standard Units and values were graded for severity, if applicable, using commonly used toxicity criteria (CTCAE version 4.03).

Grade 3, grade 4 and all grade tables of all laboratory test abnormal values were provided, and the number and percentage of subjects corresponding to the grade of each test value were calculated.

Shift tables of CTCAE grades from baseline to each visit during treatment, last result during treatment, and the worst case during treatment were provided. In the shift table, the total number of patients and the number and percentage of patients with a change in CTCAE grade at each visit were tabulated.

Those laboratory test values that could not be evaluated by CTCAE grading were analyzed using "low", "normal" and "high" based on the range of normal values provided by the local laboratory, giving a shift table from baseline to each visit during the treatment period.

All laboratory test values were tabulated separately for each laboratory parameter by patient and visit. All test values outside the laboratory normal range were tabulated separately.

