10.5.3.3 Laboratory abnormalities

All laboratory values will be converted into SI units and the severity grade calculated using appropriate common toxicity criteria for adverse events (CTCAE, version 4.03) unless otherwise indicated. The calculation of CTCAE grades will be based on the observed laboratory values only, clinical assessments will not be taken into account. CTCAE Grade 0 will be assigned for all non-missing values not graded as 1 or higher. Grade 5 will not be used. For laboratory tests where grades are not defined by CTCAE version 4.03, results will be categorized as low/normal/high based on laboratory normal ranges.

A listing of all laboratory values will be provided by laboratory parameter and by patient. All notable lab abnormalities will be presented in a separate listing.

For laboratory tests where grades are defined by CTCAE version 4.03:

- Worst post-baseline CTCAE grade (regardless of the baseline status). Each patient will be counted only once for the worst grade observed post-baseline.
- Shift tables using CTCAE grades to compare baseline to the worst on-treatment value

For laboratory tests where grades are not defined by CTCAE version 4.03:

- Shift tables using the low/normal/high classification to compare baseline to the worst on-treatment value.

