10.5.3.4 Other safety data

Safety data from other tests (e.g., vital signs) will be listed and summarized using descriptive statistics as appropriate. Notable values may be flagged. Notable/Abnormal values for safety data will be further specified in the analysis plan.

Analyses will be performed on the safety set.

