10.7 Interim analysis

Interim analysis is planned for this study for the purpose of providing a snapshot of available data to CDE for license renewal. An interim analysis will be performed in July 2017 with approximate 30 patients enrolled. This interim analysis will focus on safety and preliminary efficacy, including but not limited to:

- Safety: all adverse events observed by the data cutoff date will be summarized and listed. Separate summaries will be provided for SAE and death, respectively. Abnormal results on laboratory assessment and vital signs will be presented and listed in detail.
- Efficacy: OS and PFS observed by the data cutoff will be described using Kaplan-Meier methods and appropriate summary statistics.

Details of the analysis will be defined in statistical analysis plan (SAP).

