5.1.1 Visit Window

Treatment day is defined as the number of days on which safety/efficacy assessments are performed relative to the initiation of study drug treatment. The day on which the study drug treatment is initiated will be recorded as Study Treatment Day 1. Treatment day will be calculated as follows:

- Treatment day = date of assessment – date of initiation of study drug treatment + 1 (assessment occurs after study drug treatment)
- Treatment day = date of assessment – date of initiation of study drug treatment (assessment occurs before study drug treatment).

Since there may be deviations from the visit schedule during the actual trial operation, visit windows were created based on the scheduled treatment day of the visits in order that these deviated data could also be included in the visits for pooled analysis. If multiple assessments fall into the same visit window, the assessment closest to the scheduled treatment day in the visit window will be used in the pooled analysis. If there are multiple assessments that are equally close to the scheduled treatment date, the latest assessment will be used in the pooled analysis. The table below defines the scheduled treatment days and the width of window for visits at different assessment endpoints:

(I) Safety assessment endpoints (vital signs, laboratory tests)

Scheduled visits	Visit labels in tables/lists	Scheduled treatment days	Visit window (days)
Screening/Baseline, Visit 1	Baseline	1	≤ 1
Visit 2	Week 4	29	2 - 57
Visit 3	Week 12	85	58 - 127
Visit 4	Week 24	169	128 - 211
Visit 5	Week 36	253	212 - 295
Visit 6	Week 48	337	296 - 379
....		
Visit n	Week 12* (n-2)	$12 * (n - 2) * 7 + 1$	$12 * (n - 2) * 7 + 1 - 41 - 12 * (n - 2) * 7 + 1 + 42$

(II) Tumor assessments (only for division of the analysis visits for summary of the diameters of target lesions)

Scheduled visits	Visit labels in tables/lists	Scheduled treatment days (Day)	Visit window (days)
Screening/Baseline, Visit 1	Baseline	1	≤ 1
Visit 3	Week 12	85	2 - 127
Visit 4	Week 24	169	128 - 211
Visit 5	Week 36	253	212 - 295
Visit 6	Week 48	337	296 - 379
....		
Visit n	Week 12* (n-2)	$12 * (n - 2) * 7 + 1$	$12 * (n - 2) * 7 + 1 - 41 - 12 * (n - 2) * 7 + 1 + 42$

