5.4.4 Vital signs

Baseline is defined as the last valid assessment value prior to dosing.

The measured values of each of vital signs at baseline and different time points after baseline were described and analyzed, and the changes in measured results of each vital sign at different time points after baseline relative to baseline were given.

Results for vital signs were tabulated separately for each vital sign parameter by patient and visit.

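### For ungraded laboratory tests the SAP replaces the protocol's worst-value shift with by-visit shifts, gives no notable vital-sign criteria, and declares no change from the protocol

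*SAP*

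**What the plan says.** **Ungraded laboratory tests.** Protocol 10.5.3.3 asks for "Shift tables using the low/normal/high classification to compare baseline to the worst on-treatment value". SAP 5.4.3 classifies the same tests as low, normal or high, but ends with "giving a shift table from baseline to each visit during the treatment period". It plans no worst-value shift and no last-value shift for them.

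**Graded laboratory tests.** The same SAP section is fuller here: "Shift tables of CTCAE grades from baseline to each visit during treatment, last result during treatment, and the worst case during treatment were provided".

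**Value selection.** SAP 5.1.1 applies its safety windows to vital signs and laboratory tests. When a window holds more than one assessment, "the assessment closest to the scheduled treatment day in the visit window will be used in the pooled analysis". Ties go to the later assessment.

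**Vital signs.** Protocol 10.5.3.4 makes flagging of notable values optional, but then commits: "Notable/Abnormal values for safety data will be further specified in the analysis plan". For the interim analysis, protocol 10.7 adds: "Abnormal results on laboratory assessment and vital signs will be presented and listed in detail". SAP 5.4.4 describes the measured values by time point and says "the changes in measured results of each vital sign at different time points after baseline relative to baseline were given". It also tabulates results by patient and visit. It sets no criterion for a notable or abnormal value.

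**Declared changes.** SAP section 7, which is the place for departures from the protocol's analyses, records none.

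**The concern.** Safety is the primary objective, and the trial is descriptive with about 60 patients. In that setting a worst-value shift answers the basic laboratory question: how many patients who were normal at baseline were ever abnormal on treatment? By-visit shifts do not answer it, for two reasons.

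First, the same patient can be abnormal at several visits and different patients can be abnormal at different visits, so the by-visit counts cannot be combined into a patient count. Second, the one-value-per-window rule can drop the more extreme of two readings before the table is made.

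The gap is also undeclared. Someone who relies on section 7 would believe that the protocol's laboratory analysis is intact.

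**Working it through.** No sample size, power or event count is in dispute. The check is a comparison of the texts, a rebuild of the SAP windows, and worked examples.

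**1. Planned laboratory shifts, protocol 10.5.3.3 against SAP 5.4.3**

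| Tests | Protocol | SAP |
|---|---|---|
| CTCAE-graded | baseline to worst | baseline to each visit, last result and worst case |
| Not graded | baseline to worst | baseline to each visit |

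For graded tests the SAP meets the protocol and adds to it. For ungraded tests the required table is absent.

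**2. Windows (SAP 5.1.1).** The planned days are 29, 85, 169, 253 and 337, and the next is 421. Taking each upper limit as the midpoint to the next planned day, rounded down:
- Week 4: (29 + 85)/2 = 57, window 2–57, width 56 days
- Week 12: (85 + 169)/2 = 127, window 58–127, width 70 days
- Week 24: (169 + 253)/2 = 211, window 128–211, width 84 days
- Weeks 36 and 48: windows 212–295 and 296–379, width 84 days each

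These reproduce the SAP table exactly.

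**3. Unscheduled value.** An ungraded test is high on day 140 and normal on day 169. Both days lie in 128–211. The distances from day 169 are 29 and 0 days, so day 169 is kept. The by-visit shift shows normal; a worst-value shift would show high.

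**4. End-of-treatment value.** The visit schedule plans vital signs, hematology and liver tests at the end-of-treatment visit, but the window table has no row for that visit. Suppose a routine value falls on day 169 and treatment ends with a visit on day 190. Both lie in the Week 24 window, at distances of 0 and 21 days, so the day-190 value is not used. For a graded test the last-result shift should recover it. For an ungraded test or a vital sign, no planned summary does.

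**5. How often the extreme is dropped.** The documents give no figure. Assume that a window holds k values and that extremeness is unrelated to distance from the planned day. The most extreme value is then dropped with probability 1 − 1/k:
- k = 1: 0%
- k = 2: 50%
- k = 3: 67%
- k = 4: 75%

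This is conditional on k, and the distribution of k is unknown.

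**6. Direction.** A patient's worst on-treatment value cannot be less extreme than any value kept for a window. A count of patients ever abnormal, if taken from windowed values, can therefore equal the true count or fall below it, but cannot exceed it.

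**7. Vital-sign criteria.** Protocol 10.5.3.4 defers them to the SAP, and SAP 5.4.4 has none. Protocol 10.7 sends the interim details to the SAP, and SAP section 6 says that interim analyses follow this SAP with no separate plan. Neither document therefore defines an abnormal vital sign.

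**The case against.** The strongest reply is that little is really lost. Much of it stands.

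- **A reader might infer that extreme values vanish from the safety output. They do not.** SAP 5.4.3 lists every laboratory value by patient and visit and adds: "All test values outside the laboratory normal range were tabulated separately". SAP 5.4.4 tabulates vital signs by patient and visit. Graded tests keep grade tables and a worst-case shift.
- **Clinically important abnormalities have another route.** Under protocol 8.1.1, abnormal results that are clinically significant, cause signs or symptoms, or require therapy or a change in study medication are adverse events. Adverse events are the primary variable and are summarized at length.
- **A reader might infer that the protocol promises a notable-vital-sign analysis in the final report. It does not.** Flagging is optional. The firm commitments are to specify criteria in the SAP and to present abnormal vital signs at the interim analysis.
- **A reader might infer that by-visit means are biased toward normal.** The documents do not show this. Visits are 12 weeks apart with a one-week tolerance, so a window normally holds one scheduled value apart from an end-of-treatment visit. How often unscheduled values reach the database is not stated.
- **The laboratory scope is narrow.** The scheduled panels held in the database are hematology and liver function. Coagulation, urinalysis and other tests stay in source documents.
- **Whether the graded worst case uses all values or only windowed ones is unstated.** That is an ambiguity and not a demonstrated loss.

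None of this supplies the missing table. A listing gives no patient count or percentage, and section 7 remains inaccurate.

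**Conclusion.** The point holds as a specific and limited gap between protocol and SAP. A protocol-required shift table for ungraded laboratory tests is missing. The deferred notable vital-sign criteria are not in the SAP. Section 7 declares no change. Because of the window rule, a more extreme unscheduled or end-of-treatment value can be left out of the summary tables for ungraded tests and vital signs, while it stays in the listings.

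The size cannot be computed, because neither document says which database parameters lack CTCAE grades or how often several values share a window. The 50% to 75% range above applies only to windows with two to four values, and only under the stated independence assumption.

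The conclusion rests on reading the by-visit shift and vital-sign tables as the pooled analysis to which SAP 5.1.1 refers. The table templates are in a separate document not available here. If they contain the worst-value shift, the SAP text should say so.

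**What to change.** 1. **SAP 5.4.3:** for ungraded tests, restore the low/normal/high shift from baseline to the worst value. Present worst low and worst high separately, since a two-sided classification has two worst directions. Use all on-treatment values, including unscheduled and end-of-treatment ones.
2. **SAP 5.1.1:** state that window selection applies to by-visit summaries only and not to any worst-case derivation. This also settles the question for the graded tests.
3. **Secondary, SAP 5.4.4:** specify notable vital-sign criteria and count the patients who meet them at least once on treatment. Neither document contains such criteria, so the sponsor must supply them.
4. **SAP section 7:** if item 1 or item 3 is not adopted, record the departure from the protocol there and give the reason.

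The cost is one or two extra tables from data already collected, plus a few lines of SAP text.
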